Thyroid function	X				See Appendix 2.
Collection of post-study-treatment anticancer therapy information	X	X	X	X	Discontinuation from study must occur prior to introduction of the new agent.
Collection of survival information	X	X	X	X	In-person office visits are not required; the site may confirm survival by contacting the patient directly via telephone or other means of communication (for example, email)
Serum or urine pregnancy test	X	X	X	See instructions	Perform pregnancy test for women of childbearing potential. See Section 8.3.4 and Appendix 2. Pregnancy test required at 120 days after study discontinuation per Section 8.3.4 or 30 days following cessation of study treatment if the participant initiates new anticancer therapy.

Abbreviations: AE = adverse event; aPTT = activated partial thromboplastin time; CTCAE = Common Terminology Criteria for Adverse Events; ECOG = Eastern Cooperative Oncology Group; INR = international normalized ratio; PT = prothrombin time; SAE = serious adverse event.

- a Short-term follow-up begins when the patient and investigator agree that the patient will no longer continue study treatment.
- b Long-term follow-up begins when short-term follow-up period is completed and continues until death, study withdrawal, or the patient is lost to follow-up. In all cases, no follow-up procedures, except for pregnancy follow-up, will be performed for a patient who withdraws informed consent unless he or she has explicitly provided permission and consent.

Continued Access Schedule of Activities

	Continued Access Treatment	Continued Access Follow-up Visits ^a			
		30-Day Follow-Up	60-Day Follow-Up	90-Day Follow-Up	Notes
Visit	501-5XX	901	902	903	
Procedure					

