- Systemic glucocorticoids for any purpose other than to modulate symptoms from an AE that is suspected to have an immunologic etiology. The use of physiologic doses of corticosteroids may be approved after consultation with the Sponsor.

Note: Inhaled steroids are allowed for management of asthma.

Participants who, in the assessment of the investigator, require the use of any of the aforementioned treatments for clinical management should be removed from the study.

All treatments that the investigator considers necessary for a participant's welfare may be administered at the discretion of the investigator in keeping with the community standards of medical care.

All concomitant medications received within 28 days prior to the first dose of study treatment and up to 30 days after the last dose of study treatment should be recorded. Concomitant medications administered 30, 60, and 90 days after the last dose of study treatment should be recorded for SAEs and events of clinical interest.

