6.5.1. Palliative Medicine and Supportive Care

The need for any form of radiotherapy (including palliative) in Cycles 1-2 will be cause for early discontinuation from the study. In Cycle 3 and beyond, palliative radiotherapy will be allowed if the parameters below are met.

Palliative radiation therapy is permitted after discussion with and agreement of the Lilly CRP/CRS or designee for irradiating small areas of painful metastases that cannot be managed adequately using systemic or local analgesics. Such areas must not be an identified target lesion and must not constitute progressive disease or meet RECIST/immuno-Response Evaluation Criteria in Solid Tumors (iRECIST) criteria for progressive disease. Any symptomatic deterioration or clinical disease progression requiring, in the opinion of the investigator, other forms of specific antitumor systemic therapy will be cause for discontinuation of study therapy.

In addition, any disease progression requiring other forms of specific antitumor therapy will also necessitate early discontinuation from the study. Appropriate documentation for all forms of

premedications, supportive care, and concomitant medications must be captured on the case report form (CRF). Replacement hormonal therapy initiated before study entry will be allowed.

Patients should receive full supportive care. Hematopoietic growth factors (eg, G-CSFs) may be administered according to institutional guidelines and the local Package Insert, except in the DLT observation period. Hematopoietic growth factors will be allowed in the DLT observation period if a patient experiences neutropenia that is declared an AE. Administration of G-CSFs prior to first occurrence of neutropenia is prohibited. Blood product transfusions are permitted throughout the study.

Prophylactic antibiotic treatment should be consistent with American Society of Clinical Oncology (ASCO) guidelines (Flowers et al. 2013).

If clinically indicated at any time during the study, erythropoietin and packed red blood cell transfusions may be used according to ASCO guidelines (Rizzo et al. 2008) with adherence to the local Package Insert. All concomitant medications should be recorded throughout the patient's participation in the study.

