7.1. Discontinuation of Study Intervention

Possible reasons leading to permanent discontinuation of investigational product:

- **Participant Decision**
 - the participant or the participant's designee (for example, parents or legal guardian) requests to discontinue investigational product.

If a clinically significant finding is identified (including but not limited to changes from baseline in QTc using Fridericia's formula after enrollment, the investigator or qualified designee will determine if the participant can continue in the study and if any change in participant management is needed. This review of the ECG printed at the time of collection must be documented. Any new clinically relevant finding should be reported as an AE.

In addition, participants will be discontinued from the investigational product in the following circumstances:

- the patient becomes pregnant during the study
- the patient is significantly noncompliant with study procedures and/or treatment
- the patient, for any reason, requires treatment with another therapeutic agent that has been demonstrated to be effective for treatment of the study indication. Discontinuation from study treatment will occur prior to introduction of the new agent.
- the patient requires a dose delay of >21 days, excepted as described in Section 6.6.
- disease progression. Disease progression should be confirmed per iRECIST by the site 4 to 8 weeks after site-assessed first radiologic evidence of progressive disease in clinically stable participants. Participants, who have unconfirmed disease progression (iPUD) may continue on treatment at the discretion of the investigator until progression per iRECIST criteria is confirmed by the site. Patients continuing treatment in these circumstances must provide additional informed consent to continue therapy. A separate ICF will be created for this purpose. Any participant deemed clinically unstable should be discontinued from study treatment at first radiologic evidence of progressive disease and is not required to have repeat tumor imaging for confirmation of progressive disease by iRECIST.
- unacceptable toxicity
- the patient experiences a DLT or a DLT-equivalent toxicity
- occurrence of a venous thromboembolic event (DVT/PE) during the study
- the investigator decides that the patient should be discontinued from study treatment

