Investigators are not obligated to actively seek AEs or SAEs in participants once they have discontinued and/or completed the study (the participant disposition CRF has been completed). However, if the investigator learns of any SAE, including a death, at any time after a participant has been discharged from the study, and he/she considers the event reasonably possibly related to the study treatment or study participation, the investigator must promptly notify Lilly.

Serious adverse events, including death, caused by disease progression should not be reported unless the investigator deems them to be possibly related to LY3435151, pembrolizumab, or the combination of LY3435151 and pembrolizumab.

Suspected Unexpected Serious Adverse Reactions

Suspected unexpected serious adverse reactions (SUSARs) are serious events that are not listed in the IB and that the investigator identifies as related to investigational product or procedure. United States 21 Code of Federal Regulations (CFR) 312.32 and European Union Clinical Trial Directive 2001/20/EC and the associated detailed guidances or national regulatory requirements in participating countries require the reporting of SUSARs. Lilly has procedures that will be followed for the identification, recording, and expedited reporting of SUSARs that are consistent with global regulations and the associated detailed guidances.

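### The protocol contradicts itself on whether starting new anticancer therapy ends study participation or only study treatment, which puts survival and subsequent-therapy data at risk

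*Protocol*

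**What the plan says.** **Leaving the study.**
- Protocol 1.3, post-treatment follow-up schedule, comment on the row that records anticancer therapy given after study treatment: "Discontinuation from study must occur prior to introduction of the new agent".
- Protocol 6.5: participants who, in the investigator's assessment, "require the use of any of the aforementioned treatments for clinical management should be removed from the study". The restricted list includes antineoplastic systemic therapy.
- Protocol 6.5.1: "any disease progression requiring other forms of specific antitumor therapy will also necessitate early discontinuation from the study".

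**Leaving study treatment only.**
- Protocol 7.1, for a patient who needs another effective agent: "Discontinuation from study treatment will occur prior to introduction of the new agent".
- Protocol 6.5.1, immediately before the sentence quoted above: symptomatic deterioration or clinical progression requiring "other forms of specific antitumor systemic therapy will be cause for discontinuation of study therapy".
- Protocol 7.2 lists the reasons for leaving the study. New anticancer therapy is not among them.

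**Data that the plan expects afterwards.**
- The follow-up schedule marks survival and subsequent anticancer therapy at visits 801, 802, 803 and 804-X. Its footnote b says that long-term follow-up "continues until death, study withdrawal, or the patient is lost to follow-up".
- SAP 5.4.8 and 5.4.8.3 plan a Kaplan-Meier analysis of OS as an exploratory objective. SAP 5.4.5 plans a summary of postdiscontinuation therapies.

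**Safety follow-up.**
- The schedule collects SAEs for 90 days, shortened to 30 days after cessation if new anticancer treatment starts.
- Protocol 7.2 asks patients who leave the study early, for whatever reason, to complete AE and safety follow-up. Protocol 8.3 says: "Investigators are not obligated to actively seek AEs or SAEs in participants once they have discontinued" or completed the study.

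**The concern.** The protocol treats stopping study intervention (7.1) and leaving the study (7.2) as different events with different consequences. Footnote b ends long-term follow-up at study withdrawal but not at the start of new therapy. Which word applies therefore decides whether a patient is still followed.

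The schedule comment also undercuts its own row: a patient would have to leave the study before receiving the therapy that the row exists to record. A site that follows it literally would stop collecting survival and subsequent therapy in the patients who go on to more treatment. Sites that read it differently would produce uneven follow-up within one trial. Survival status not collected at the time may not be recoverable later.

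**Working it through.** **1. Text comparison.** Three places say study (schedule comment, 6.5, one sentence of 6.5.1). Two say study treatment or study therapy (7.1, the other sentence of 6.5.1). Section 7.2 is silent on new therapy. Under the literal schedule reading, no section restores survival collection: 7.2 keeps only AE and safety follow-up, and the vital-status search in 7.3 is for patients lost to follow-up.

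**2. SAE window.** Suppose new therapy starts, and the patient leaves the study, on day t after cessation. The schedule already limits SAE collection to day 30 in that case.
- Days at risk = 30 − t for t < 30, otherwise 0.
- Example: t = 14 gives 30 − 14 = 16 days.
- If 7.2 is followed, even these days are kept. They are lost only if 8.3 is taken to prevail.

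**3. Deaths lost to OS.** The plan gives no figure to reproduce. The SAP states no censoring rule for OS, so I take a patient who leaves as censored on leaving. All inputs are assumptions:
- time to progression exponential, median 3 months: a = ln 2/3 = 0.2310 per month;
- post-progression survival exponential, median 8 months with new therapy (b = ln 2/8 = 0.0866) and 3 months without (rate a again);
- a proportion u of patients starts new therapy and leaves at progression; the cut is at 24 months, and every site follows the literal wording.

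Probability of death by 24 months:
- with new therapy: 1 − [a·e^(−24b) − b·e^(−24a)]/(a − b) = 1 − (0.2310 × 0.125 − 0.0866 × 0.0039)/0.1444 = 0.802;
- without: 1 − (1 + 24a)·e^(−24a) = 1 − 6.545 × 0.0039 = 0.974.

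Share of deaths lost = 0.802u / [0.802u + 0.974(1 − u)]:

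| Uptake u | Calculation | Lost |
|---|---|---|
| 20% | 0.160/(0.160 + 0.779) | 17% |
| 40% | 0.321/(0.321 + 0.584) | 35% |
| 60% | 0.481/(0.481 + 0.390) | 55% |

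If new therapy starts 1 month after progression, deaths within that month are still seen. About 1 − 2^(−1/8) = 0.083 of the new-therapy patients die in it, so 0.802 becomes about 0.719. The losses are then 0.4 × 0.719/0.905 = 32% and 0.6 × 0.719/0.871 = 50%.

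**4. Direction of bias at 12 months.** Under the same assumptions, 12-month survival is 0.528 with new therapy and 0.236 without.
- True OS: 0.4 × 0.528 + 0.6 × 0.236 = 0.35 at 40% uptake; 0.6 × 0.528 + 0.4 × 0.236 = 0.41 at 60%.
- Expected Kaplan-Meier value with exit at progression: e^(−12a)·[1 + (1 − u)·12a]^(1/(1 − u)), which is 0.32 at 40% and 0.40 at 60%.
- If post-progression survival is instead 5 months in both groups, true OS is 0.38 and the expected estimate at 60% uptake is 0.52 (hazard integrated numerically).

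The estimate is slightly too low in the first setting and clearly too high in the second.

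**The case against.** The strongest reply is that this is loose wording and not a rule. The comment sits in a row that makes sense only if patients are still followed, survival is marked at the same visits, 7.2 does not make new therapy a reason to leave, and the SAP plans analyses that need the data. The schedule is loose elsewhere too: its pregnancy-test comment counts 120 days from study discontinuation and cites 8.3.4, which counts from the end of study treatment. This stands as evidence of intent. A reader might infer that the protocol means to stop survival follow-up at new therapy; the documents do not support that. The defect is an instruction that sites can misapply.

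A reader might also infer that SAE follow-up would end altogether once the patient leaves. That goes too far. Section 7.2 asks for safety follow-up to be completed, the schedule already shortens the window to 30 days, and 8.3 removes only the duty to look actively. What remains is a conflict between 7.2 and 8.3 over at most 30 days. It deserves settling because Protocol 4.1.1.4 uses AEs from the 90-day follow-up in choosing the recommended dose.

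Finally, the consequences are limited. OS is exploratory, the primary endpoints are DLTs and safety, and PFS already censors at new therapy (Protocol 9.4.3.2; SAP Table JZIA.5.2). This lowers the priority but does not remove the contradiction.

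**Conclusion.** The contradiction is established from the text alone. Followed literally, the schedule comment would end survival and subsequent-therapy collection when new therapy starts, and so undermine the exploratory OS analysis and the postdiscontinuation therapy summary.

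The size depends on uptake and on assumptions from outside the documents: 17% to 55% of deaths by 24 months for uptake of 20% to 60%, somewhat less if new therapy is delayed after progression. These are upper figures in the sense that they assume full literal compliance. Lost information is the robust effect. A reader might infer a bias in OS in a known direction; the calculations do not support that, since its sign changes with post-progression survival. The SAE exposure is at most 30 days per patient. Overall this is a real inconsistency of modest priority.

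**What to change.** Reconcile the schedule comment in 1.3 with Sections 6.5, 6.5.1, 7.1, 7.2 and 8.3, so that the same term (study, or study treatment) is used for the same event. Whatever the sponsor decides on the clinical rule, add one explicit statement on data: starting new anticancer therapy does not end study participation for data collection. Survival and subsequent-therapy collection continue through visits 804-X, and SAE collection continues for the window that the schedule already sets. In 8.3, say how the absence of a duty to seek events fits with the safety follow-up required by 7.2.

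The cost is wording in the next amendment. The visits already exist, and the schedule lets sites confirm survival by telephone or email.

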1.3.1. Sampling Schedules for Pharmacokinetics and Biomarkers and Safety

Schedule for Phase 1a

Sampling Day	Time Relative to End of LY3435151 Infusion	PK Collection	ECG	Serum Cytokines and Exploratory Biomarkers	Whole blood for Flow Profile ^d	Immunogenicity Sample	Plasma Sample for Exploratory Biomarkers	Stool Sample for Microbiota Analysis ^g	Hematology CBC (local testing) ^e
Baseline ≤7 days prior C1D1			X				X	X	
Cycle 1 Day 1	predose ^h	X	X ^c	X	X	X			
Cycle 1 Day 1	1hr ± 15mn	X	X ^c						
Cycle 1 Day 1	3hr ± 30mn	X							X
Cycle 1 Day 2	24hr ± 4hr	X	X ^c	X					X
Cycle 1 Day 4	72hr ± 24hr	X		X					X
Cycle 1 Day 8	168hr ± 24hr	X				X			
Cycle 1 Day 15	336hr ± 24hr	X							
Cycle 2 Day 1	predose ^h	X		X	X	X			
Cycle 2 Day 1	1hr ± 15mn	X	X ^c						
Cycle 2 Day 1	3hr ± 30mn	X							
Cycle 3 Day 1	predose ^h	X		X	X	X	X	X	

Sampling Day	Time Relative to End of LY3435151 Infusion	PK Collection	ECG	Serum Cytokines and Exploratory Biomarkers	Whole blood for Flow Profile ^d	Immunogenicity Sample	Plasma Sample for Exploratory Biomarkers	Stool Sample for Microbiota Analysis ^g	Hematology CBC (local testing) ^e
Cycle 3 Day 1	1hr ± 15mn	X	X ^c						
Cycle 4 Day 1	predose ^h	X							
Cycle 5-n Day 1	predose ^h	X				See footnote ^b			
If IRR, at onset, resolution and 30 days following IRR ^a		X				X			
When/if any DLT or DLT equivalent occurs		X							
EOT ^f		X		X		X	X	X	
V801		X		X		X	X		
V802		X				X			
V803		X		X		X			

Abbreviations: C = Cycle; CBC = complete blood count; D = Day; DLT = dose-limiting toxicity; ECG = electrocardiogram; EOT = end of treatment; hr = hours; IL = interleukin; IRR = infusion-related reaction; mn = minutes; PBMC = peripheral blood mononuclear cell; PK = pharmacokinetics; V = Visit.

- a Exploratory hypersensitivity immunogenicity and PK samples may be analyzed for markers of basophil/mast cell activation (eg, tryptase), immune complex formation (eg, C3 levels) and cytokine release (eg, IL-6) as appropriate for the clinical presentation.
- b Immunogenicity sample will be collected every fourth cycle from C1 (eg, C5D1, C9D1)
- c Central triplicate ECGs
- d Not applicable for Cohort A1
- e See Section 1.3 for more hematology sample time points.
- f End of Treatment (EOT) is the same as study treatment discontinuation, which happens when the subject and the investigator agree that the subject will no longer continue study treatment.
- g may be collected ± 3 days of scheduled time point
- h predose samples should be collected prior to LY3435151 dosing and, if applicable, pembrolizumab dosing

Schedule for Phase 1b

Sampling Day	Time Relative to End of Infusion	PK Collection	ECG	Serum Cytokines and Exploratory Biomarkers	Whole Blood for Flow Profile	Immunogenicity Sample	Plasma Sample for Exploratory Biomarkers	Stool Sample for Microbiota Analysis ^e
Baseline ≤ 7 days prior C1D1			X				X	X
Cycle 1 Day 1	predose ^f	X	X ^e	X	X	X		
Cycle 1 Day 1	1hr ± 15mn	X	X ^e					
Cycle 2 Day 1	predose ^f	X		X	X	X		
Cycle 2 Day 1	1hr ± 15mn	X	X ^e					
Cycle 3 Day 1	predose ^f	X		X	X	X	X	X
Cycle 3 Day 1	1hr ± 15mn	X	X ^e					
Cycle 4 Day 1	predose ^f	X		X				
Cycle 5-n Day 1	predose ^f	X				See footnote ^b		
If IRR, at onset, resolution, and 30 days following IRR ^a		X				X		
When/if any DLT equivalent occurs		X						
EOT ^d				X			X	X
V801		X		X		X	X	

Sampling Day	Time Relative to End of Infusion	PK Collection	ECG	Serum Cytokines and Exploratory Biomarkers	Whole Blood for Flow Profile	Immunogenicity Sample	Plasma Sample for Exploratory Biomarkers	Stool Sample for Microbiota Analysis ^e
V802		X				X		
V803		X				X		

Abbreviations: C = Cycle; D = Day; DLT = dose-limiting toxicity; ECG = electrocardiogram; EOT = end of treatment; hr = hours; IL = interleukin; IRR = infusion-related reaction; mn = minutes; PBMC = peripheral blood mononuclear cell; PK = pharmacokinetics; V = Visit.

- ^a Exploratory hypersensitivity immunogenicity and PK samples may be analyzed for markers of basophil/mast cell activation (eg, tryptase), immune complex formation (eg, C3 levels) and cytokine release (eg, IL-6) as appropriate for the clinical presentation.
- ^b Immunogenicity sample will be collected every fourth cycle from C1 (eg, C5D1, C9D1)
- ^c Central triplicate ECGs
- ^d End of Treatment (EOT) is the same as study treatment discontinuation, which happens when the subject and the investigator agree that the subject will no longer continue study treatment.
- ^e may be collected ± 3 days of scheduled time point
- ^f predose samples should be collected prior to LY3435151 dosing and, if applicable, pembrolizumab dosing

2. Introduction

2.1. Study Rationale

Recent clinical success revealed the potential for potent antitumor activity in a variety of solid tumors by targeting T-lymphocyte inhibitory pathways using monoclonal antibodies that block inhibitory receptors on the surface of T cells. The anti-cytotoxic T lymphocyte-associated antigen-4 (CTLA-4) antibody ipilimumab was approved by the US Food and Drug Administration (FDA) and the European Medicines Agency for the treatment of patients with advanced melanoma in 2011 (EMA 2019; FDA 2019). Blockade of the programmed cell death protein 1 (PD-1) or programmed death-ligand 1 (PD-L1) pathway demonstrated durable responses in 30% to 35% of patients with advanced melanoma (Topalian et al. 2012; Hamid et al. 2013), which led to FDA approval of pembrolizumab and nivolumab in 2014 and European Commission approval of pembrolizumab in 2015. Despite remarkable clinical activity of PD-1/PD-L1 inhibitors demonstrated in several clinical studies in patients with a wide variety of malignancies, there are limitations to their efficacy and many patients do not respond to these therapies. For example, only 10-40% unselected patients of various solid tumors (including non-small cell lung cancer, urothelial carcinoma, classic Hodgkin lymphoma, head and neck squamous cell carcinoma [HNSCC], renal cell carcinoma, Merkel cell carcinoma, hepatocellular carcinoma [HCC], and gastric carcinomas) show clinical response to anti-PD-1/PD-L1 monotherapy, and some initially responding patients eventually developed resistance and disease progression (Zou et al. 2016; Kim et al. 2017).

During checkpoint blockade with anti-CTLA-4 and anti-PD-1/PD-L1 inhibitors, multiple other checkpoint inhibitors may become coordinately upregulated. The compensatory upregulation of these alternative checkpoint receptors, such as LAG-3, TIGIT, TIM-3, CD160, and VISTA axes, have been demonstrated in preclinical models (Syn et al. 2017) including head and neck cancer (Shayan et al. 2017), metastatic ovarian cancer (Huang et al. 2017), metastatic melanoma (Benci et al. 2016), lung adenocarcinoma (Koyama et al. 2016), and prostate cancer (Gao et al. 2017). This could be a result of interferon signaling and activation of various pathways in tumor-infiltrating lymphocytes (TILs), which can negatively regulate T cell activity and eventually lead to treatment failure (Syn et al. 2017). Inhibition of these molecules alone or in combination may increase the frequency of objective responses and achieve efficacy in cancer types that have thus far been largely refractory to CTLA-4 and/or PD-1 blockade. Many clinical trials are currently underway to test antibodies against these inhibitory pathways, both as monotherapy and combination therapy strategies (Sharma et al. 2017).

CD226 is a co-stimulatory receptor, expressed on T, NK, platelets, DC, monocytes, and other immune cells. Ligands of CD226, PVR (CD155) and PVRL2 (CD112), are shared with the co-inhibitory receptors TIGIT and CD96. Activation of CD226 leads to proliferation, differentiation and cytokine production in NK (innate) and T (adaptive) cells in primary human cells. Anti-CD226 antagonist antibodies have shown to completely block the efficacy of anti-PD-L1 combination therapy in syngeneic mouse tumor models demonstrating the role of CD226 in antitumor immunity (Johnston et al. 2014). We propose to include a combination of CD226 agonist with PD-1 antagonist (pembrolizumab) including subjects that are not eligible for approved therapy, including those with no PD-L1 expression as measured by

immunohistochemistry (IHC). The potential benefit could be induced by CD226 agonist modulation of the TIL state or changes to the tumor environment and PD-L1 expression to increase the likelihood of response to pembrolizumab that is not induced by pembrolizumab alone. This may be in addition to the predicted additive effect of CD226 agonist with PD-1 antagonist in those patients that express PD-L1 and do not respond to pembrolizumab due to additional resistance mechanisms as discussed.

Combinations of anti-TIGIT antibodies with a clinically validated checkpoint inhibitor such as PD-1 or PD-L1 antibodies are also being actively investigated for treatment of many other types of cancers as monotherapy and in combinations (Solomon and Garrido-Laguna 2018).

In addition, in order to appropriately select patients who are more likely to benefit from PD-1/L1 inhibitors, various biomarkers have been investigated to predict clinical responses (Kim et al. 2017), such as CD8+ T cells in the tumor microenvironment (Tumeh et al. 2014), high tumor mutational loads (Rizvi et al. 2015), neoantigen heterogeneity (McGranahan et al. 2016), and PD-L1 expression in the tumor microenvironment (Tumeh et al. 2014). Among these suggested biomarkers, PD-L1 expression in pretreatment tumor samples has been most extensively studied and confirmed to be correlated with better clinical outcome in various malignancies (Powles et al. 2014; Borghaei et al. 2015; Chow et al. 2016; Daud et al. 2016). Recently, TILs have become the focus of many studies. As reported in recent literature, increased levels of TILs in women receiving neoadjuvant chemotherapy were associated with increased complete response (CR) rate and survival benefit in both triple-negative breast cancer (TNBC) and human epidermal growth factor receptor 2 (HER2)-positive breast cancers (Denkert et al. 2017). In another study, researchers assessed TILs and PD-L1 expression as prescreening enrichment biomarkers to identify patients with better clinical benefit from checkpoint inhibitors. The response rate in patients with TILs $\geq 7\%$ was 32% versus 9% in patients with TILs $< 7\%$ (Fisher's exact test $p = 0.06$) (Martin-Liberal et al. 2018). Therefore, quantifying TILs may help select patients for immunotherapy in early clinical trials from an otherwise unselected population (Teng et al. 2015).

The predicted mechanism of action of LY3435151 suggests that it will primarily act within the tumor environment where TILs are inhibited as described above by either sequestration of CD226 ligand or loss of the ligand's expression on tumor cells. While CD226 is frequently expressed on CD8+ TILs, not all tumors have TILs. As a result, TIL-negative tumors may not demonstrate a clinical response. The presence of TILs is therefore potentially essential for the drug effect in tumors. Based on this hypothesis, Study J1Q-MC-JZIA (JZIA) will:

- 1) Select solid tumors associated with TIL positivity.
- 2) Evaluate the presence of TILs prior to therapy to determine the impact of TIL presence and quantity on drug response.
- 3) Limit treatment to patients that are found to have pre-existing TILs upon analysis of the pre-treatment biopsy (Cohort D3 only).

The combined approach of selecting patients likely to have pre-existing TILs or using TIL selection based on pre-treatment biopsies will potentially increase the probability of observing a response in this study.

Study JZIA is a multicenter, open-label dose-escalation followed by a randomized dose-expansion study designed to investigate the safety and tolerability of LY3435151 when administered as monotherapy and in combination with pembrolizumab for the treatment of patients with advanced solid tumors associated with TIL positivity:

- TNBC (Stanton et al. 2016)
- Gastric adenocarcinoma (including gastroesophageal junction adenocarcinoma) (Steele et al. 2018)
- HNSCC (Steele et al. 2018)
- Squamous cervical carcinoma (Enwere et al. 2017)
- High-grade serous ovarian carcinoma (Stumpf et al. 2009)
- HCC (Xiao-Yan Cai et al. 2006)
- Undifferentiated pleomorphic sarcoma (UPS) and leiomyosarcoma (LMS; Pollack et al. 2017)

